**Table 3.6-1 Schedule of Evaluations (Cohorts 1-5 and Dose-Expansion Weekly Schedule): Screening and Treatment Periods**

Evaluations	Screening a	Cycle 1					Cycle 2 and Every Cycle Thereafter			Every 2 Cycles, Beginning With Cycle 3	End of Treatment
		Days 1, 8	Days 2, 9	Days 3, 10	Day 15	Day 22	Day 1	Day 8	Day 15		
Cohort 1		Day 1	Day 2	Day 3	Day 8	Day 15					
Cohorts 2 through 5 and dose-expansion weekly schedule		Day 1	Day 2	Day 3	Day 8	Day 15					
Written Informed Consent and HIPAA	X										
Verify Eligibility Criteria	X	X b									
Medical History	X										
Serum βhCG	X										
Urine βhCG		X b					X				
MEDI-575 Administration		X			X	X	X	X	X		
Physical Examination c	X	X b					X			X	X d
Height	X										
Weight	X	X b					X				X
Vital Signs	X	X e		X	X e	X e	X e	X e	X e		X
12-lead ECG f	X	X g					X h				X
Hematology q	X	X i		X	X i	X i	X i	X i	X i		X
Serum Chemistry j	X	X i		X	X i	X i	X i	X i	X i		X

**Table 3.6-1 Schedule of Evaluations (Cohorts 1-5 and Dose-Expansion Weekly Schedule): Screening and Treatment Periods**

Evaluations	Screening a	Cycle 1					Cycle 2 and Every Cycle Thereafter			Every 2 Cycles, Beginning With Cycle 3	End of Treatment
		Days 1, 8	Days 2, 9	Days 3, 10	Day 15	Day 22	Day 1	Day 8	Day 15		
		Day 1	Day 2	Day 3	Day 8	Day 15					
Routine Urinalysis	X	X			X	X	X	X	X		X
AE/SAE Assessment	X k	X		X	X	X	X	X	X	X	X
Concomitant Medications	X	X		X	X	X	X	X	X	X	X
CT or MRI Scans	X									X	X d
Karnofsky Performance Status	X	X b					X				X d
MEDI-575 Serum Concentration		X l	X m	X n	X o	X o	X o	X o	X o		X
Anti-MEDI-575 Antibodies		X b, h					X h				X
Serum Tumor Biomarkers (as relevant to tumor type)	X						X				
Circulating Plasma Biomarker Analysis		X l	X m	X n	X o	X o	X o	X o	X o		X
Circulating Tumor Cells	X						X h				X r
RNA Analysis	X						X h				X
DNA Analysis (Optional)	X										

**Table 3.6-1 Schedule of Evaluations (Cohorts 1-5 and Dose-Expansion Weekly Schedule): Screening and Treatment Periods**

Evaluations	Screening a	Cycle 1					Cycle 2 and Every Cycle Thereafter			Every 2 Cycles, Beginning With Cycle 3	End of Treatment
		Days 1, 8	Days 2, 9	Days 3, 10	Day 15	Day 22	Day 1	Day 8	Day 15		
Cohort 1											
Cohorts 2 through 5 and dose-expansion weekly schedule		Day 1	Day 2	Day 3	Day 8	Day 15					
Archived Tumor Sample (Optional)	X p										

a To occur within 28 days prior to the first dose of MEDI-575.

b Study Day 1 only.

c Complete physical examination at screening, after every 2 cycles, and at the end of treatment; a focused examination at the start of each cycle.

d These procedures do not need to be repeated if they have been performed within 14 days of disease progression or treatment discontinuation.

e Monitor vital signs prior to infusion, at 15, 30, and 60 minutes (±5 minutes) post initiation of infusion, at the completion of infusion (±5 minutes), and 30 and 60 minutes (±5 minutes) post completion of infusion.

f ECG equipment (with instant print-out and electronic transmission capabilities) and training will be provided to all study sites. All ECGs performed during the study will be obtained in triplicate, ie, 3 ECGs are to be obtained within a 5-minute time interval.

g Prior to infusion, at the time of completion of infusion (± 5 minutes), 2 hours post completion of infusion (± 15 minutes), and 6 hours (± 15 minutes) post completion of infusion. All ECGs should be done prior to PK draw for corresponding time points.

h Prior to the initiation of infusion.

i Prior to infusion on day indicated.

j Includes AST/ALT, total bilirubin, creatinine (and creatinine clearance at screening), alkaline phosphatase, sodium, potassium, chloride, phosphorus, calcium, glucose, magnesium, albumin, and LDH.

k Only those AEs assessed by the investigator as protocol/procedure related. All SAEs are to be reported.

l Prior to infusion, immediately post completion of infusion (± 5 minutes), and 2 hours (± 15 minutes) and 6 hours (± 15 minutes) post completion of infusion.

**Table 3.6-1 Schedule of Evaluations (Cohorts 1-5 and Dose-Expansion Weekly Schedule): Screening and Treatment Periods**

Evaluations	Screening a	Cycle 1					Cycle 2 and Every Cycle Thereafter			Every 2 Cycles, Beginning With Cycle 3	End of Treatment
Cohort 1		Days 1, 8	Days 2, 9	Days 3, 10	Day 15	Day 22	Day 1	Day 8	Day 15		
Cohorts 2 through 5 and dose-expansion weekly schedule		Day 1	Day 2	Day 3	Day 8	Day 15					

m 24 hours (± 2 hours) post completion of infusion on Study Day 1, Cycle 1 (all dose cohorts), and Study Day 9, Cycle 1 (Dose Cohort 1, only).

n 48 hours (± 2 hours) post completion of infusion on Study Day 1, Cycle 1 (all dose cohorts), and Study Day 10, Cycle 1 (Dose Cohort 1, only).

o Prior to and immediately (±5 minutes) post completion of infusion.

p If archived tumor sample is available and subject provides consent, collect and ship per instructions in Specimen Collection Manual.

q Includes complete blood count (CBC), differential, and platelet count.

r Only for dose-expansion weekly schedule.

**Table 3.6-2 Schedule of Evaluations (Cohorts 6 and 7, and Dose-Expansion Every 3-Week Schedule): Screening and Treatment Periods**

Evaluations	Screening a	Cycle 1					Cycle 2 and Every Cycle Thereafter	Every 2 Cycles, Beginning With Cycle 3	End of Treatment
		Day 1	Day 2	Day 3	Day 8	Day 15	Day 1		
Written Informed Consent and HIPAA	X								
Verify Eligibility Criteria	X	X b							
Medical History	X								
Serum βhCG	X								
Urine βhCG		X b					X		
MEDI-575 Administration		X					X		
Physical Examination c	X	X b					X	X	X d
Height	X								
Weight	X	X b					X		X
Vital Signs	X	X e		X	X	X	X e		X
12-lead ECG f	X	X g					X h		X
Hematology q	X	X i		X	X	X	X i		X
Serum Chemistry j	X	X i		X	X	X	X i		X
Routine Urinalysis	X	X			X	X	X		X
AE/SAE Assessment	X k	X		X	X	X	X	X	X

**Table 3.6-2 Schedule of Evaluations (Cohorts 6 and 7, and Dose-Expansion Every 3-Week Schedule): Screening and Treatment Periods**

Evaluations	Screening a	Cycle 1					Cycle 2 and Every Cycle Thereafter	Every 2 Cycles, Beginning With Cycle 3	End of Treatment
		Day 1	Day 2	Day 3	Day 8	Day 15	Day 1		
Concomitant Medications	X	X		X	X	X	X	X	X
CT or MRI Scans	X							X	X d
Karnofsky Performance Status	X	X b					X		X d
MEDI-575 Serum Concentration		X l	X m	X n	X	X	X o		X
Anti-MEDI-575 Antibodies		X b, h					X h		X
Serum Tumor Biomarkers (as relevant to tumor type)	X						X		
Circulating Plasma Biomarker Analysis		X l	X m	X n	X	X	X o		X
Circulating Tumor Cells	X						X h		X
RNA Analysis	X						X h		X
DNA Analysis (Optional)	X								
Archived Tumor Sample (Optional)	X p								

**Table 3.6-2 Schedule of Evaluations (Cohorts 6 and 7, and Dose-Expansion Every 3-Week Schedule): Screening and Treatment Periods**

Evaluations	Screening a	Cycle 1					Cycle 2 and Every Cycle Thereafter	Every 2 Cycles, Beginning With Cycle 3	End of Treatment
		Day 1	Day 2	Day 3	Day 8	Day 15	Day 1		
a To occur within 28 days prior to the first dose of MEDI-575 b Study Day 1 only. c Complete physical examination at screening, after every 2 cycles, and at the end of treatment; a focused examination at the start of each cycle. d These procedures do not need to be repeated if they have been performed within 14 days of disease progression or treatment discontinuation. e Monitor vital signs prior to infusion, at 15, 30, and 60 minutes ( $\pm 5$ minutes) post initiation of infusion, at the completion of infusion ( $\pm 5$ minutes), and 30 and 60 minutes ( $\pm 5$ minutes) post completion of infusion. f ECG equipment (with instant print-out and electronic transmission capabilities) and training will be provided to all study sites. All ECGs performed during the study will be obtained in triplicate, ie, 3 ECGs are to be obtained within a 5-minute time interval. g Prior to infusion, at the time of completion of infusion ( $\pm 5$ minutes), 2 hours post completion of infusion ( $\pm 15$ minutes), and 6 hours ( $\pm 15$ minutes) post completion of infusion. All ECGs should be done prior to PK draw for corresponding time points. h Prior to the initiation of infusion. i Prior to infusion on day indicated. j Includes AST/ALT, total bilirubin, creatinine (and creatinine clearance at screening), alkaline phosphatase, sodium, potassium, chloride, phosphorus, calcium, glucose, magnesium, albumin, and LDH. k Only those AEs assessed by the investigator as protocol/procedure related. All SAEs are to be reported. l Prior to infusion, immediately post completion of infusion ( $\pm 5$ minutes), 2 hrs ( $\pm 15$ minutes) and 6 hrs ( $\pm 15$ minutes) post completion of infusion. m 24 hours ( $\pm 2$ hours) post completion of infusion on Study Day 1, Cycle 1 (all dose cohorts). n 48 hours ( $\pm 2$ hours) post completion of infusion on Study Day 1, Cycle 1 (all dose cohorts). o Prior to and immediately ( $\pm 5$ minutes) post completion of infusion. p If archived tumor sample is available and subject provides consent, collect and ship per instructions in Specimen Collection Manual. q Includes complete blood count (CBC), differential, and platelet count.									

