### 3.5.3 Investigational Product Preparation

The dose of investigational product for administration must be prepared by the Investigational Product Manager/site pharmacist using aseptic technique. Detailed instructions regarding investigational product preparation can be found in the Investigational Product Manual that will be provided to the Investigational Product Manager/site pharmacist.

The dose of investigational product will be calculated by the Investigational Product Manager/site pharmacist on the basis of the subject's body weight (obtained prior to the first administration of MEDI-575 in each treatment cycle) and the subject's dose level. The dose volume of MEDI-575 will be calculated using the following formula:

$$\text{Dose Volume (mL)} = \text{Dose Level (mg/kg)} \times \text{Subject Weight (kg)} \div \text{Concentration (10 mg/mL)}$$

MEDI-575 is prepared for administration by dilution into the appropriate volume of normal saline to a final volume of 250 mL. The final volume will be 500 mL for subjects enrolled in the every 3-week dosing schedule.

Prior to dilution into normal saline, the required number of vials for each dose of MEDI-575 must equilibrate separately at room temperature (23°C to 27°C; 73°F to 81°F) for 90 minutes.

To prepare the IV bag, the volume of normal saline equivalent to the calculated dose volume of MEDI-575 is removed from the IV bag, and then the calculated dose volume of MEDI-575 is added to the IV bag containing the remaining saline.

MEDI-575 should be administered immediately as a 60-minute (Cohorts 1 through 5 and weekly dosing schedule of the dose-expansion phase) or 90-minute (Cohorts 6 and 7 and every 3-week dosing schedule of the dose-expansion phase) IV infusion.

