**Cycle 1, Study Day 1 (and Study Day 8 for Dose Cohort 1 only)**

- 1) Verify eligibility criteria (Study Day 1 only, for all dose cohorts and dose-expansion phase)
- 2) Update screening history and physical examination findings (any new findings since screening; Study Day 1, only, for all dose cohorts and dose-expansion phase)
- 3) Assess for SAEs and protocol-related AEs
- 4) Update concomitant medications
- 5) Obtain body weight for dosing calculations (Study Day 1, only, for all dose cohorts and dose-expansion phase)
- 6) Blood collection prior to infusion of MEDI-575
  - Chemistry panel (AST/ALT, total bilirubin, creatinine, alkaline phosphatase, sodium, potassium, chloride, phosphorus, calcium, glucose, magnesium, albumin, and LDH)
  - Hematology (CBC, differential, and platelet count)
  - Serum concentration of MEDI-575
  - Circulating plasma biomarker analysis
  - Anti-MEDI-575 antibodies (Study Day 1, only, for all dose cohorts and dose-expansion phase)
- 7) Routine urinalysis
- 8) Urine  $\beta$ hCG (Study Day 1, only, for all dose cohorts and dose-expansion phase)
- 9) Karnofsky performance status (Study Day 1, only, for all dose cohorts and dose-expansion phase)
- 10) Focused physical examination (Study Day 1, only, for all dose cohorts and dose-expansion phase)

- 11) 12-lead ECG (prior to infusion), at the time of completion of infusion ( $\pm$  5 minutes), 2 hours ( $\pm$  15 minutes) post completion of infusion, and 6 hours ( $\pm$  15 minutes) post completion of infusion. All ECGs performed will be obtained in triplicate (ie, 3 ECGs should be obtained within approximately a 5-minute time interval). All ECGs should be done prior to PK draw for the corresponding time point.
- 12) Vital signs prior to infusion of MEDI-575 (temperature, blood pressure, pulse rate, respiratory rate)
- 13) Administration of MEDI-575
- 14) Monitor for AEs and SAEs
- 15) Monitor vital signs at 15, 30, and 45 minutes ( $\pm$  5 minutes) post initiation of infusion, at the completion of infusion ( $\pm$  5 minutes), and 30 and 60 minutes ( $\pm$  5 minutes) post completion of infusion
- 16) Blood collection immediately after and 2 and 6 hours ( $\pm$  15 minutes) post completion of infusion
  - Serum concentration of MEDI-575
  - Circulating plasma biomarker analysis

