#### **5.5.1 Pharmacokinetics of MEDI-575**

The PK of MEDI-575 will be assessed using the variables of AUC, (which will be calculated by the trapezoidal rule),  $C_{\max}$ ,  $T_{\max}$ ,  $t_{1/2}$ , and CL. These parameters will be obtained by non-compartmental methods. Linearity in the PK of MEDI-575 will be assessed from  $t_{1/2}$  and dose-normalized AUC and  $C_{\max}$ . Descriptive statistics will be provided by dose cohort.

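### The end-of-infusion PK draw is called post completion but carries a ±5 minute window, so a draw during the infusion complies: a small downward error that a 0 to +5 minute window removes

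*Protocol*

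**What the plan says.** Table 3.6-1 (weekly schedule, 60-minute infusions) has two footnotes for this sample:

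- Footnote l covers Cycle 1 Day 1, and Day 8 in Cohort 1. After the pre-dose sample it asks for draws "immediately post completion of infusion (± 5 minutes), and 2 hours (± 15 minutes) and 6 hours (± 15 minutes) post completion of infusion". Footnotes m and n add samples at 24 and 48 hours.
- Footnote o covers the other dosing days: "Prior to and immediately (±5 minutes) post completion of infusion". No further sample is taken on those days.

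Table 3.6-2 (every 3-week schedule, 90-minute infusions) repeats both windows. Section 3.5.3 gives the infusion lengths.

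The visit lists in Section 3.6 also put the draw after the infusion and print ±5 minutes. These are Cycle 1 Study Days 8 and 15 (15 and 22 in Cohort 1), and Study Days 1, 8 and 15 of Cycle 2 onward. Item 16 of the Cycle 1, Study Day 1 list differs. It reads "Blood collection immediately after and 2 and 6 hours" and then prints only ±15 minutes, the window that footnote l gives to the 2- and 6-hour draws.

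Section 5.5.1 names Cmax and Tmax as PK variables, obtained by non-compartmental methods. It adds: "Linearity in the PK of MEDI-575 will be assessed from" half-life and dose-normalized AUC and Cmax.

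**The concern.** The words post completion and after put the draw once the dose is in. The minus half of the window permits it while drug is still running in. A site that draws 5 minutes early complies with the table, but its sample misses part of the dose.

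A non-compartmental Cmax is the largest observed value, so no model corrects for an early draw. The error runs one way: an early draw understates the peak, and a late draw barely changes it for a slowly cleared antibody. Dose-normalized Cmax is one of three linearity measures, so the error touches a stated secondary analysis.

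**Working it through.** The protocol states no figure for this error, so there is none to reproduce.

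**Inputs from the protocol.** Infusion length T is 60 or 90 minutes (Section 3.5.3). The window is ±5 minutes (footnotes l and o). The 2-hour sample has ±15 minutes (footnote l). Dosing intervals are 7 or 21 days. Cohorts have 3 to 6 subjects.

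**Assumptions.** The protocol gives no human half-life; I take 1 to 15.4 days. The upper end follows from its targets in Section 2.4 (average 250 µg/mL, trough above 150 µg/mL, every 3 weeks). With one compartment, kτ/(exp(kτ) − 1) = 150/250 gives kτ = 0.947, and 21 × 0.693/0.947 = 15.4 days. It is indicative only, because 150 is a lower bound for the trough. Between-subject CV of Cmax is assumed at 20% to 40%. The infusion rate is constant.

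**Step 1: a lone first-dose sample, 5 minutes early.** With negligible elimination during infusion, shortfall = 5/T.

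- 60 minutes: 5/60 = 8.3% (8.2% to 8.3% with elimination in the model)
- 90 minutes: 5/90 = 5.6% (5.4% to 5.6%)

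**Step 2: the same sample, 5 minutes late.** Shortfall = 1 − 2^(−5 min/half-life). This is 0.02% at 15.4 days and 0.24% at 1 day, whatever the infusion length.

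**Step 3: Cycle 1 Day 1.** Cmax is the larger of the early draw and the 2-hour sample, taken at 2 h 15 min as the worst case. The later sample is low by 1 − 2^(−2.25 h/half-life).

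| Half-life | 2 h 15 min sample low by | Cmax low by, 60 min | Cmax low by, 90 min |
|---|---|---|---|
| 15.4 days | 0.42% | 0.42% | 0.42% |
| 10 days | 0.65% | 0.65% | 0.65% |
| 5 days | 1.29% | 1.29% | 1.29% |
| 2 days | 3.2% | 3.2% | 3.2% |
| 1 day | 6.3% | 6.3% | 5.4% |

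Where the 2-hour sample is the larger, Tmax reads about 2 hours late. A two-compartment check (distribution half-life 6 to 24 hours, 30% to 50% of the dose in the fast phase) puts the 2 h 15 min sample 2% to 11% low. In the least favorable case it no longer helps, and the loss returns to the early draw's own 8.1% (60 minutes) or 5.3% (90 minutes).

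**Step 4: footnote-o days at steady state.** Drug left from earlier doses dilutes the error. Shortfall ≈ (5/T) × (1 − 2^(−τ/half-life)). At 10 days:

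- weekly: 8.33% × (1 − 0.616) = 3.2%
- every 3 weeks: 5.56% × (1 − 0.233) = 4.3%

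Model results:

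| Half-life | Weekly, 60 min | Every 3 weeks, 90 min |
|---|---|---|
| 2 days | 7.5% | 5.5% |
| 5 days | 5.2% | 5.2% |
| 10 days | 3.2% | 4.3% |
| 15.4 days | 2.3% | 3.4% |

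**Step 5: scale.** The standard error of a cohort mean is CV/√n. For n = 3 this is 20%/1.73 = 11.5% to 40%/1.73 = 23.1%. For n = 6 it is 8.2% to 16.3%.

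**Step 6: a one-sided window.** With 0 to +5 minutes only Step 2 applies: 0.02% to 0.24%, or about 0.5% with the fastest distribution phase tried.

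**The case against.** The strongest reply is that the text already fixes the order. Every place says post or after, so a sensible site draws after completion and treats 5 minutes as tolerance. On Cycle 1 Day 1 the triplicate ECG must also precede the PK draw, which pushes it later. The Specimen Collection Manual, not at hand, may say more. This makes early draws less likely but does not exclude them: the completion ECG has its own ±5 minutes, so ECG and draw can both precede the end of infusion.

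The reply is also right about consequence. The 2-hour sample recovers most of Cmax on Cycle 1 Day 1. Cohorts 1 through 5 share one infusion length and one window, so the rule itself builds in no dose trend. Linearity also rests on AUC and half-life, and the planned summaries are descriptive. One reservation remains: Section 1.5 expects a very short half-life at 0.5 mg/kg, where the 2-hour sample protects least.

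Two stronger readings are tempting, and the documents support neither:

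- A reader might infer that 60-minute cohorts are biased more than 90-minute cohorts. That holds for a lone first-dose sample. In the one-compartment model it disappears on Cycle 1 Day 1 at half-lives of 2 days or more, and at steady state the order can reverse.
- A reader might apply the ±15 minutes of item 16 to the end-of-infusion draw and compute much larger losses. Footnote l gives that draw ±5 minutes; item 16 merely fails to repeat it.

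**Conclusion.** A minor point that stands on wording. As written, a PK draw up to 5 minutes before the end of infusion complies, against the protocol's own description of the sample, and only that half of the window does appreciable harm.

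Worst cases are 8.3% or 5.6% for a lone first-dose sample. For Cmax on Cycle 1 Day 1 they are about 0.4% to 3% at half-lives of 15.4 down to 2 days, about 6% at 1 day and about 8% with fast distribution. On footnote-o days at steady state they are about 2% to 7.5% for half-lives of 15.4 down to 2 days. All assume a draw at the very edge of the window; the average error depends on how often sites draw early, which is unknown. Half-life, distribution and CV are assumptions.

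The Cmax figures lie below the assumed standard error of a cohort mean, narrowly so in the least favorable case (8.1% against 8.2% at n = 6 and CV 20%). The PK objective is not undermined. The case for change is that the error is one-directional, avoidable and free to remove.

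**What to change.** In footnotes l and o of Tables 3.6-1 and 3.6-2, replace ±5 minutes for the end-of-infusion draw with 0 to +5 minutes after completion. Make the same change in the post-infusion blood items of the visit lists for Cycle 1 Study Days 8 and 15 (15 and 22 in Cohort 1) and for Study Days 1, 8 and 15 of Cycle 2 onward. In item 16 of the Cycle 1, Study Day 1 list, state 0 to +5 minutes for the first draw and keep ±15 minutes for the 2- and 6-hour draws. The plasma biomarker sample shares these footnotes and visit items and moves with the PK draw. The ECG-first rule still works, because the ECG window opens before completion.

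The cost is wording only: no extra sample or visit. Section 1.4 reports enrollment through Cohort 5, so the gain falls on Cohorts 6 and 7 and the expansion phase. For subjects already sampled, draws before completion can be flagged if actual infusion-stop and draw times were recorded.

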**Table 3.6-3 Schedule of Evaluations: Follow-up Period**

All Cohorts and Dose Expansion	Follow-up/Post-therapy	
	30 Days	Every 3 Months
Physical Examination	X	
Weight	X	
12-lead ECG	X	
Vital Signs	X	
Hematology	X	
Serum Chemistry	X	
Routine Urinalysis	X	
Urine $\beta$ hCG	X	
AE/SAE Assessment	X	
Concomitant Medications	X	
CT or MRI Scans		X a
Focused Physical Examination		X a
Karnofsky Performance Status	X	X a
Subsequent Anticancer Therapy	X	X
Survival Status		X
MEDI-575 Serum Concentration	X	
Anti-MEDI-575 Antibodies	X	X b
Circulating Plasma Biomarker Analysis	X	

a For subjects who discontinue treatment due to reasons other than disease progression or initiation of alternative anticancer therapy, disease evaluations will be performed every 3 months until documentation of disease progression, initiation of alternative anticancer therapy, or the end of study (defined as 1 year after the last subject enters the study).

b This test will be performed at 3 months post dose only.

## Screening

*Note: All screening procedures must be performed within 28 days before the first dose of investigational product (Study Day 1), unless otherwise specified. The screening evaluations may be carried out over more than 1 visit. Written informed consent and HIPAA (applies to covered entities in the USA only) must be obtained prior to performing any study-related procedure, including screening evaluations. However, if evaluations that have been performed for other purposes prior to informed consent are otherwise suitable for use as screening evaluations, those studies need not be repeated if the subject/legal representative consents to allow use.*

- 1) Written informed consent and HIPAA
- 2) Obtain SID from sponsor
- 3) Verify eligibility criteria
- 4) Perform medical history
- 5) Perform complete physical examination, including height and weight  
Note: Items 4 and 5 above are designed to collect information on the subject once written informed consent has been obtained to start the screening process. Any new physical examination finding, symptom, disease, or untoward medical event that begins after written informed consent has been obtained, but before receipt of investigational product, that is not related to a protocol requirement must be added to the baseline medical history or physical examination records.
- 6) Perform 12-lead ECG. All ECGs performed will be obtained in triplicate (ie, 3 ECGs should be obtained within approximately a 5-minute time interval).
- 7) Routine urinalysis
- 8) Vital signs
- 9) Evaluation of disease
  - CT or MRI scans
  - Karnofsky performance status
- 10) Blood collection for screening
  - Chemistry panel (AST/ALT, total bilirubin, creatinine, creatinine clearance, alkaline phosphatase, sodium, potassium, chloride, phosphorus, calcium, glucose, magnesium, albumin, and lactate dehydrogenase [LDH])
  - Hematology (complete blood count [CBC], differential, and platelet count)
  - Serum  $\beta$ hCG
  - Serum tumor biomarker analysis (as relevant to tumor type)

- DNA analysis (optional)
  - Circulating tumor cell analysis
  - RNA analysis
- 11) Assess for SAEs and protocol-related AEs
  - 12) Record concomitant medications
  - 13) If archived tumor tissue is available and subject provides consent to release, ship block to sponsor per instructions in Specimen Collection Manual.
  - 14) Complete enrollment paperwork and fax to sponsor within 48 hours of the anticipated time of first dosing with MEDI-575.

